5.1.6. Emergency Unblinding

Unblinding of treatment assignment for a subject may be necessary due to a medical emergency, rescue therapy (Section 5.2.2), or any other significant medical event (eg, pregnancy).

In the case of an emergency, the Investigator has the sole responsibility for determining if unblinding is warranted. The Investigator is required to follow the specific steps outlined in the unblinding procedure in the Study Reference Manual. Prior to unblinding, it is suggested that the Investigator contact the Sponsor and discuss the intended unblinding with the Medical Monitor or appropriate Insmed Incorporated study personnel (if this does not interfere with emergency treatment). In all cases of unblinding, the date, including justification for unblinding, must be fully documented and signed by the Investigator and written notification provided to the Sponsor. The originally signed copy is maintained in the study file at the site, and a copy is provided to the Sponsor or its designee. The date and reason for the unblinding is also entered in the study file and any associated AE reports. The Investigator can obtain the identity of the study drugs dispensed to a subject through IWRS.

5.1.7. Labeling and Packaging

Subjects will receive kits containing vials of ALIS or ELC and the nebulizer system. The nebulizer system is manufactured by PARI Respiratory Equipment, Richmond, VA, a subsidiary of PARI Pharma GmbH, Germany.

AZI tablets and ETH tablets will be sourced commercially. The packaging will vary depending on the manufacturer.

Labels will be prepared in accordance with GMP requirements and local regulatory guidelines. Label text will be translated into local language.

5.1.8. Storage

ALIS and ELC must be stored at 2°C to 8°C (36°F to 46°F); do not freeze. All sourced commercial drug supply, specifically Azithromycin 250 mg tablets and Ethambutol 100 mg and Ethambutol 400 mg tablets, should be stored according to the temperature ranges indicated on the commercial packaging.

At the study site, all study drugs must be stored in a secured place with restricted access.

5.1.9. Dispensing of Study Drugs

At visits specified in [Table 4](#), subjects will be dispensed adequate study drugs to allow for daily dosing, including extra supply for potential study visit scheduling delays. Study drugs may be dispensed directly to the subject's home by courier if dispensing at the site is not feasible.

5.1.10. Drug Accountability

Drug accountability records will be maintained for all clinical supplies. All transactions will be recorded on the drug accountability records including shipment receipts and study subject doses. All transactions will be recorded on a real-time basis.

The pharmacy or responsible study staff will maintain detailed documentation of the number and identification of vials and dispensing units with copies of these documents to be provided to the Sponsor at the end of the study. All used and unused study drugs will be maintained by the site until inventoried by the Clinical Trial Monitor. Upon completion of the drug inventory by the Study Monitor, the used and any unused vials and tablets will be disposed of in accordance with instructions provided to sites and according to site destruction policies. Documentation of destruction should be provided to the Sponsor.

Accountability of the nebulizer system will be maintained and tracked at the site. Subjects must return the nebulizers to the study site at EOT. Additional instructions for handling the disposal or return of the devices will be provided to the sites and according to site destruction policies.

5.2. Concomitant Medications

Any medications the subject takes other than study drugs, including all vaccinations received, on or after the first dose of study drug are considered concomitant medications and will be collected and documented in the study eCRF.

5.2.1. Bronchodilator Therapy

If a subject is being treated with or started on bronchodilator therapy for management of underlying lung disease, the subject should be pretreated with a bronchodilator prior to ALIS or ELC administration throughout the study. If a subject is not on bronchodilator therapy and experiences a TEAE or SAE that is a respiratory symptom, the Investigator may consider pretreatment with a short acting bronchodilator prior to the ALIS or ELC administration. If a subject is pretreated with a bronchodilator prior to the ALIS or ELC administration, the subject should consistently pretreat moving forward in the study. Data will be collected on the concomitant medication eCRF page.

5.2.2. Rescue Therapy

Rescue therapy is defined as any change from the randomized treatment (ALIS + background regimen or ELC + background regimen) as prescribed in the study (includes drug, dose, frequency, route of administration) due to progression of MAC lung infection. Rescue therapy does not include changes from randomized treatment (eg, removal or replacement of drug) due to intolerance or AEs from study drugs.

If at any time during the study the Investigator believes that a subject has worsened clinically (eg, progressive worsening of signs/symptoms), the Investigator will determine the cause of the clinical deterioration (eg, intercurrent illness, noncompliance with pulmonary therapies, or progression of the MAC lung infection) and should contact the Medical Monitor. The clinical symptoms and cause should be documented in the subject's source documentation. If non-urgent intervention is required, the Investigator will optimize concomitant therapy and will contact the subject within 7 days of presentation via a telephone visit to reassess the subject. Within 14 days of determination of clinical worsening, the subject should make all attempts to return to the study site for an unscheduled visit for in-clinic assessment. However, if the subject is unable to return for the unscheduled visit, the assessment of change in signs/symptoms can be confirmed with a telephone visit. At that visit, the Investigator will then confirm the cause of the worsening signs/symptoms and should contact the Medical Monitor. If the Investigator confirms that the cause of the worsening in signs/symptoms is due to progression of MAC lung infection and rescue therapy is warranted, the Investigator will contact the Sponsor to unblind the subject from treatment assignment (Section 5.1.6). All contacts with the Medical Monitor should be documented in the subject's source documentation.

Subjects who receive rescue therapy will stop randomized treatment (ALIS + background regimen or ELC + background regimen), be treated by local standard of care or as recommended by the Investigator, and will continue with their remaining scheduled study visits.

Data will be collected on the appropriate eCRF pages.

5.3. Prohibited Medications and Medications with Limited Use

Subjects are prohibited from using any inhaled antibiotics or any aminoglycosides with activity against MAC, such as streptomycin or kanamycin at Screening and throughout the study. The use of these drugs should not be initiated during the study period unless as determined necessary by the Investigator. Subjects are also prohibited from using any antibiotics for the treatment of MAC lung infection (besides study drugs), unless required as rescue therapy (Section 5.2.2).

Other prohibited medications include those contraindicated with concomitant use with azithromycin and ethambutol per local labeling guidance. The reason for use must be documented in the eCRF. Some antibiotics used for the treatment of concomitant conditions that may have activity against MAC may be used, but not for more than 14 consecutive days.

Any questions about prohibited medications should be discussed with the Medical Monitor. A list of prohibited medications and medications with limited use for the study is provided in [Table 2](#). Refer to local labeling guidance for other prohibited medications with concomitant use with azithromycin and ethambutol.

Table 2: List of Prohibited Medications and Medications with Limited Use

PROHIBITED Drugs	LIMITED USE Drugs (not more than 14 consecutive days)
Aminoglycosides: Amikacin, Kanamycin, Streptomycin	Other Macrolides: Erythromycin, Clarithromycin, etc.
Rifamycins: Rifampin, Rifampicin, Rifabutin, Rifamycin, etc.	Fluoroquinolones: Levofloxacin, Moxifloxacin, Sitafloxacin, Ciprofloxacin, etc.
Bedaquiline	Linezolid, Tedizolid
Clofazimine	Tigecycline, Eravacycline, Omadacycline
Isoniazid	Any other antibiotic with activity against MAC
Ethambutol (only allowed per protocol)	--
Azithromycin (only allowed per protocol)	--

5.4. Precautionary Medications

Chronic anti-inflammatory therapy (eg, high-dose ibuprofen, prednisone \leq 10 mg/day or the equivalent) is permitted if the regimen remains unaltered for at least 28 days preceding Day 1/Baseline and throughout the study. The doses should not change except for safety reasons or as needed for medical management of the subject.

Although systemic exposure to amikacin is low after ALIS administration, precaution should be taken if subjects require the following systemic medications that may have possible interactions with amikacin, including, but not limited to the following: potent diuretics (such as ethacrynic acid and furosemide), beta lactam antibiotics (such as penicillins and cephalosporins); bisphosphonates; platinum compounds and thiamine.

The following may have possible interactions with azithromycin or ethambutol: digoxin, colchicine, and coumarin anticoagulants. Antacids should not be taken simultaneously with azithromycin or ethambutol. Azithromycin or ethambutol must be administered at least 1 hour before or 2 hours after antacid is taken.

Local labeling guidance for azithromycin and ethambutol must be consulted.

Examples of precautionary medications for ALIS are provided in [Table 3](#).

Table 3: List of Examples of Precautionary Medications for ALIS

Name of Drug	Clinical Symptoms/ Treatment	Mechanism/ Risk Factor(s)
Potentially nephrotoxic blood substitutes such as Dextran Hydroxyethyl starch, etc.	Since there is a risk that nephrotoxicity occurs or is aggravated, concomitant use should be avoided. When nephrotoxicity occurs, drug should be discontinued and appropriate treatment be implemented such as renal dialysis, etc.	The mechanism of action is not completely clear but there are reports that the combination leads to deposits of aminoglycoside antibiotics in blood and to vacuolization of the proximal tubular epithelium.
Loop diuretics Ethacrynic acid Furosemide Azosemide, etc.	Since both drugs may cause or aggravate nephro- and ototoxicity, concomitant use should be avoided.	The mechanism of action is not completely clear but there are reports that the combination leads to increased blood concentration and renal deposits of aminoglycoside antibiotics.
Nephrotoxic and ototoxic drugs such as Vancomycin, Enviomycin, Platinum-containing anticancer drugs (cisplatin, carboplatin, nedaplatin), etc.	Since both drugs may cause or aggravate nephro- and ototoxicity, concomitant use should be avoided.	Both drugs are nephrotoxic/ ototoxic but the mechanism of action of the interaction is not known.
Anesthetics Muscle relaxants Tubocurarine Pancuronium bromide Tolperisone Botulinum Type A toxin products, etc.	Risk of respiratory suppression. If respiratory suppression occurs, choline esterase inhibitor or calcium preparation, etc. should be administered as appropriate.	Both drugs have a neuro-muscular inhibitory effect. Concomitant use will aggravate this effect.
Nephrotoxic drugs Cyclosporine A Amphotericin B, etc.	Risk that renal impairment occurs or is aggravated.	Both drugs are nephrotoxic but the mechanism of the interaction is not known.

6. STUDY PROCEDURES

6.1. Schedule of Assessments

The Schedule of Assessments is presented in [Table 4](#).

COVID-19 restrictions and/or concerns may impact subject attendance at in-clinic visits (Section 6.3). In the event subjects are restricted from attending in-clinic visits or if subjects have concerns regarding travel and attending in-clinic visits (due to potential public health concerns), the site should contact the Sponsor on how to conduct the scheduled assessments, and decisions should be documented in the source documentation.

The PRO instruments will be provided to the subject in electronic format on a computer tablet and should be conducted at approximately the same time of day at the specified timepoints.

All PRO assessments must be completed prior to other study assessments (eg, physical examination, vital signs, laboratory assessments, audiology, etc) with the exception of sputum collection. If the subject produces their best sputum samples first thing in the morning prior to being able to attend a clinic visit, the subject should consistently collect sputum samples first, then proceed with PRO assessments throughout the study.

At each in-clinic visit, the subject will complete the PRO assessments in the order listed below. The approximate time to complete each assessment is provided; these are conservative estimates based on different studies and actual time may be less than indicated.

1. QOL-B (~10-15 minutes)
2. PROMIS F-SF 7a (~8-12 minutes)
3. EXACT (~3 minutes)
4. EXACT-RS (~3 minutes)
5. SGRQ (~10 minutes)
6. FACIT– Fatigue (~8-12 minutes)
7. PGI-S– Respiratory (~1 minute)
8. PGI-S– Fatigue (~1 minute)

All remaining assessments must be completed prior to administration of study drugs. If additional assessments for monitoring are recommended per local labeling guidance, the site should complete unscheduled assessments.

Table 4: Schedule of Assessments

INS-415	Screening	Treatment Phase						
		In-Clinic		Non In-Clinic ^a	In-Clinic	Non In-Clinic ^a	In-Clinic	
		Baseline/ Day 1	Month 1	Month 2	Month 3, 5	Month 4	Month 6 (EOT) ^b	Month 7 (EOS) ^c
		(V1)	(V2)	(V3)	(V4)	(V5, 7)	(V6)	(V8)
Visit Window	Approximately -70 days to -1 day	--	(±7)	(±7)	(±7)	(±7)	(±7)	(±7)
Informed consent	X	--	--	--	--	--	--	--
Pregnancy test ^d	X	X	X	X	X	X	X	X
Randomization	--	X	--	--	--	--	--	--
QOL-B ^e	X	X	--	--	X	--	X	X
PROMIS F-SF 7a ^e	X	X	--	--	X	--	X	X
EXACT ^e	X	X	--	--	--	--	--	X
EXACT RS ^e	X	X	--	--	--	--	--	X
SGRQ ^e	X	X	--	--	--	--	--	X
FACIT-Fatigue ^e	X	X	--	--	--	--	--	X
PGI-S Respiratory ^e	X	X	--	--	X	--	X	X
PGI-S Fatigue ^e	X	X	--	--	X	--	X	X
Actigraphy ^f		X	X		X	--	X	X
Medical history	X		--	--	--	--	--	--
Physical examination ^g	X	X	--	--	X	--	X	X
Vital signs and pulse oximetry ^h	X	X	X	--	X	--	X	X
FEV ₁	X	X	--	--	--	--	--	--
Audiology ^j	X ⁱ		--	--	--	--	X	--

INS-415	Screening	Treatment Phase						
		In-Clinic		Non In-Clinic ^a	In-Clinic	Non In-Clinic ^a	In-Clinic	
		Baseline/ Day 1	Month 1	Month 2	Month 3, 5	Month 4	Month 6 (EOT) ^b	Month 7 (EOS) ^c
		(V1)	(V2)	(V3)	(V4)	(V5, 7)	(V6)	(V8)
Visit Window	Approximately -70 days to -1 day	--	(±7)	(±7)	(±7)	(±7)	(±7)	(±7)
ECG ^j	X							
Ophthalmic Exam ^j	X							
Concomitant medications	X	X	X	X	X	X	X	X
AE assessment	X ^k	X ^l	X	X	X	X	X	X
Sputum collection for microbiology ^m	X	X	X	X	X	X	X	X
Chemistry ⁿ	X	X	X	--	X	--	X	X
Hematology ⁿ	X	X	X	--	X	--	X	X
Urinalysis ⁿ	X	X	X	--	X	--	X	X
CRP ⁿ	--	X	X	--	X	--	X	X
CT scan of chest (by local read) ^o	X	--	--	--	--	--	--	--
Send sputum collection containers home	X	X	X	--	X	--	X	--
Administer study drugs at site or at home ^p	--	X	X	--	X	--	--	--
eDiary for study drugs compliance	--	X	X	X	X	X	X	--
Dispense study drugs ^q	--	X	X	--	X	--	--	--
Collection of study drugs	--	--	X	--	X	--	X	--

AE = adverse event; CRP = C-reactive protein; CT = computed tomography; EOS = end of study; EOT = end of treatment; EXACT = EXacerbations of Chronic Pulmonary Disease Tool; ERS = EXACT Respiratory Symptoms; FACIT-Fatigue = Functional Assessment of Chronic Illness Therapy; FEV1 = forced expiratory volume in 1 second; ICF = informed consent form; MAC = *Mycobacterium avium* complex; PGI-S = Patient Global Impression of Severity; PRO = patient-reported outcomes; PROMIS Fatigue Short Form 7a = Patient-Reported Outcome Measure Information System Fatigue-Short Form 7a; QOL-Bronchiectasis = Quality of Life Questionnaire – Bronchiectasis; SAE = serious adverse event; SGRQ = St George Respiratory Questionnaire; WOCBP = women of child-bearing potential.

- a. If applicable; may be converted to clinic visits if needed due to local requirements
- b. If a subject discontinues ALIS or ELC, the subject will have reason for ALIS or ELC withdrawal recorded and return at the next scheduled visit to complete the EOT visit assessments. The subject will remain on the other study drugs (AZI and/or ETH) and continue with the next scheduled study visit. The subject will complete a Month 6 visit when they reach Month 6.
- c. Subjects will remain off all study drugs and should avoid initiating any new medical or non-medical therapies for MAC lung infection.
- d. Serum pregnancy testing will be performed on WOCBP at Screening. A urine pregnancy test (at least 25 mIU/mL sensitivity) must be performed for all WOCBP at all subsequent visits starting at Baseline. Women not of childbearing potential are defined as postmenopausal (ie, amenorrheic for at least 12 months), or surgically or naturally sterile.
- e. All PRO assessments will be performed prior to any other assessments (with the exception of sputum collection) and administration of study drugs and should be performed in the following order: QOL-B, PROMIS F-SF 7a, EXACT, EXACT-RS, SGRQ, FACIT-Fatigue, PGI-S-Respiratory, and PGI-S-Fatigue.
- f. Collection of data is continuous. Data will be retrieved by study staff at in-clinic visits.
- g. The physical examination will also include measurement of body weight; the measurement of height, without shoes, will only be done at Screening. All physical examinations should be performed prior to administration of study drugs.
- h. Vital signs and pulse oximetry will be assessed prior to administration of study drugs.
- i. The Baseline audiology examination must be performed during Screening or on Day 1 before administration of study drugs and evaluated by the Investigator.
- j. Tests may be performed if required by local labeling guidance; Investigators should perform all monitoring according to local label
- k. Only SAEs will be collected after the ICF is signed until Baseline.
- l. At Baseline, AEs will be assessed only after administration of study drugs. Any AE that has occurred prior to the first dose must be included in the subject's medical history, including any AEs that occur within the Screening period.
- m. Sputum cultures will be collected by study personnel at in-clinic study visits prior to administration of study drugs. Subjects will provide and ship sputum cultures at non in-clinic visits. Subjects who are not able to ship sputum samples may bring the samples to the clinic site. Two sputum samples will be obtained from each subject at each assessment; subjects will produce 1 sputum sample on the day prior to the scheduled visit and 1 sputum sample on the day of the visit prior to dosing with study drugs. At Screening, subjects will produce 1 sputum sample on the first day of the visit and 1 sputum 1 week later. The second sputum sample provided at Screening can be produced any time during the week following the Screening visit.
- n. All laboratory testing should be performed prior to the administration of study drugs at in-clinic visits. Laboratory testing will **not** be performed at the Month 5 visit.
- o. A prior chest CT scan may be used as a subject's Screening measurement if this CT scan was obtained within 6 months from the subject's Screening visit. Subjects who do not have a chest CT scan within 6 months prior to Screening will be required to obtain a scan during Screening.
- p. Study drugs may be administered at home during a home care visit (if applicable), if administration at site is not feasible
- q. Study drugs may be dispensed directly to the subject's home by a courier if dispensing at site is not feasible

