7.1.1. Quality of Life Questionnaire – Bronchiectasis

The QOL-B is a validated, self-administered, reported outcome questionnaire used to assess symptoms, functioning, and health related quality of life in adults with non-CF bronchiectasis (Quittner et al., 2015). It measures outcomes over a recall period of 1 week. The questionnaire contains 37 items on 8 scales (physical, role, vitality, emotional, social, treatment burden, health perception, and respiratory) (Appendix 1).

The QOL-B questionnaire will be completed at study visits in the order specified in Section 6.1 and Schedule of Assessments (Table 4). Subjects will self-administer the questionnaire electronically. The QOL-B questionnaire will be the first assessment to be conducted at the specified study visits (with the exception of sputum collection, if applicable).

Each of the 37 items is scored from 1 to 4, and each of the 8 scale scores is standardized on a 0 to 100-point scale, with higher scores representing fewer symptoms or better functioning and quality of life. Scores are calculated for the 8 domains: physical, role, vitality, emotional, social, treatment burden, health perception, and respiratory.

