8. EFFICACY ASSESSMENTS

8.1. Sputum Culture

Microbiological assessment of sputum specimens will be used for secondary efficacy measurements.

During the study, pre-dose expectorated or induced sputum samples (approximately 2 mL) are required at study visits specified in the Schedule of Assessments (Table 4). To improve the probability of obtaining a good sputum specimen, 2 sputum samples will be obtained from each subject at each assessment; subjects will provide 1 sputum sample on the day prior to the scheduled visit, and 1 sputum sample on the day of the visit prior to dosing with study drugs. At Screening, subjects will provide 1 sputum sample on the day of the visit and 1 sputum during the week following the Screening visit. If a subject is unable to produce sputum spontaneously, sputum may be induced. If after induction, a subject is still unable to produce sputum despite reasonable efforts, this will be recorded as non-productive at that time point. It is recommended to schedule an in-clinic visit as a backup to non in-clinic visits in case the subject is not able to spontaneously produce sputum at home. If a subject is unable to spontaneously produce sputum at home on the day prior to the scheduled visit, the subject should then come into the clinic for sputum induction on the scheduled visit. The induction should be performed within the specified visit window (Table 4). At the scheduled visit, once sputum is collected (spontaneously or by induction), study drugs can be administered. If the subject produces their best sputum samples first thing in the morning prior to being able to attend a clinic visit, the subject should consistently collect sputum samples first, then proceed with PRO assessments and other assessments throughout the study.

Sterile, leak proof, non-wax, disposable plastic containers labeled with 2 subject identifiers will be used to collect specimens aseptically to avoid contamination. Sputum samples should be refrigerated, not frozen, until shipped to the central microbiology laboratory as soon as possible to avoid overgrowth by contaminating normal flora. No fixative or preservatives are to be used with sputum samples. Detailed instructions for collecting, processing, and shipping sputum specimens will be provided in the site laboratory manual. Subjects will be provided with instructions for collecting, processing, and shipping sputum specimens for samples collected at non in-clinic visits.

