**APPENDIX C. EXACT**

Blue figures: as coded in eCRF

	0. Not at all
	1. Slightly
1. Did your chest feel congested today?	2. Moderately
	3. Severely
	4. Extremely
	0. Not at all
	1. Rarely
2. How often did you cough today?	2. Occasionally
	3. Frequently
	4. Almost constantly
	0 0. None at all
	1 1. A little
3. How much mucus (phlegm) did you bring up when coughing today?	01 1. Some
	2 2. A great deal
	3 3. A very great deal
	NOTE: Score "A little" and "Some" the same.
	0. Not at all
	1. Slightly
4. How difficult was it to bring up mucus (phlegm) today?	2. Moderately
	3. Quite a bit
	4. Extremely
	0. Not at all
	1. Slight
5. Did you have chest discomfort today?	2. Moderate
	3. Severe
	4. Extreme
	0. Not at all
	1. Slightly
6. Did your chest feel tight today?	2. Moderately
	3. Severely
	4. Extremely

Blue figures: as coded in eCRF

	0	0. Not at all
	1	1. Slightly
7. Were you breathless today?	2	2. Moderately
	3	3. Severely
	4	4. Extremely
	0	0. Unaware of breathlessness
	1	1. Breathless during strenuous activity
8. Describe how breathless you were today:	2	2. Breathless during light activity
	3	3. Breathless when washing or dressing
	03	3. Present when resting
		NOTE: Score "Breathless when washing or dressing" and "Present when resting" the same.
	0	0. Not at all
	1	1. Slightly
9. Were you short of breath today when performing your usual personal care activities like washing or dressing?	2	2. Moderately
	3	3. Severely
	03	3. Extremely
	4	4. Too breathless to do these
		NOTE: Score "Severely" and "Extremely" the same.
	0	0. Not at all
	1	1. Slightly
10. Were you short of breath today when performing your usual indoor activities like cleaning or household work?	2	2. Moderately
	3	3. Severely
	03	3. Extremely
	003	3. Too breathless to do these
		NOTE: Score "Severely," "Extremely," and "Too breathless to do these" the same.
	0	0. Not at all
	1	1. Slightly
11. Were you short of breath today when performing your usual activities outside the home such as yard work or errands?	2	2. Moderately
	3	3. Severely
	03	3. Extremely
	003	3. Too breathless to do these
		NOTE: Score "Severely," "Extremely," and "Too breathless to do these" the same.

Blue figures: as coded in eCRF

	0. Not at all
	1. Slightly
12. Were you tired or weak today?	2. Moderately
	3. Severely
	4. Extremely
	0. Not at all
	1. Slightly
13. Last night, was your sleep disturbed?	2. Moderately
	3. Severely
	4. Extremely
	0 0. Not at all
	1 1. Slightly

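### The PROs-first rule exempts all sputum collection and sets no order between in-clinic induction and the questionnaires, leaving cough and mucus items (EXACT/E-RS above all) open to an avoidable error of unknown size and direction

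*Protocol*

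**What the plan says.** Three places in the protocol put the PROs ahead of everything else and then exempt sputum. Table 4 footnote e: "All PRO assessments will be performed prior to any other assessments (with the exception of sputum collection) and administration of study drugs". The text of Section 6.1 has the same carve-out, "with the exception of sputum collection". Section 7.1.1 makes the QOL-B the opening assessment, "with the exception of sputum collection, if applicable".

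Only one sputum-first situation is described. It begins "If the subject produces their best sputum samples first thing in the morning prior to being able to attend a clinic visit" and goes on to say that "the subject should consistently collect sputum samples first, then proceed with PRO assessments throughout the study". Section 8.1 repeats this case.

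Section 8.1 also allows induction when a subject cannot produce sputum spontaneously. Its one ordering rule for induction is relative to dosing: "At the scheduled visit, once sputum is collected (spontaneously or by induction), study drugs can be administered". Table 4 footnote m requires one sample on the day before the visit and one on the visit day before dosing, with collection by study personnel at in-clinic visits.

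Among the instruments, EXACT item 3 (SAP Appendix C) asks "How much mucus (phlegm) did you bring up when coughing today", and item 2 asks about cough on the same day. QOL-B items 30 and 31 ask about coughing and mucus over the past week (SAP Appendix A). The respiratory PGI-S names cough and mucus over the past week (SAP Appendix G).

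**The concern.** The primary objective is to validate PRO instruments, and Section 1.3 says the validated instrument will be used to assess clinical benefit in a separate study. Measurement conditions therefore matter more here than in most trials. The protocol recognises this: it fixes the order of eight questionnaires and keeps even vital signs and physical examination until after them. Yet it leaves open the one procedure closest in content to the items. Induction is done to obtain sputum that the subject could not otherwise bring up. A subject who has just been induced and is then asked about cough and mucus that day may report the procedure as a symptom.

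If the order varies, PRO scores carry noise that has nothing to do with disease. If induction before the PROs is more or less common at Month 7 than at Baseline, mean change shifts, and the meaningful-change estimate is a mean change score (Protocol 10.5.2). If its frequency differs by conversion status, the converter contrast used as an additional anchor shifts as well.

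**Working it through.** **Plan's own figure (context only).** Protocol 10.1 claims at least 80% power for a 7-point converter versus non-converter difference with N = 100. Inputs: correlation ρ = 0.40, conversion rate p of 50 to 70%, missing data 0 to 20%, two-sided 0.05. Total SD = 7·p(1−p)/(ρ·φ(z_p)). Within-group SD = √(SD² − 49·p(1−p)). At p = 0.5 the SDs are 10.97 and 10.39, and noncentral-t power with no missing data is 0.915. At p = 0.7 they are 10.57 and 10.07, and power with 20% missing is 0.803. The claim reproduces and is not disputed.

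**Step 1: the order rules side by side.**

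| Place in protocol | Rule | Limited by place or method of collection? |
|---|---|---|
| 6.1 text | PROs before all else, sputum excepted | No |
| Table 4 footnote e | Same, and before study drug | No |
| 7.1.1 | QOL-B leads, sputum excepted where applicable | No |
| 6.1 and 8.1, morning sample | Sample, then PROs, consistently | Yes: sample produced before attending |
| Table 4 footnote m | Visit-day sample before dosing | No; order set against dosing only |
| 8.1, induction | Allowed when spontaneous production fails | No; order set against study drug only |

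Induction just before the PROs is therefore permitted but not required. A site may equally do the PROs first. The instruction to be consistent belongs to the morning-sample case and does not cover induction.

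**Step 2: which scores are exposed.** EXACT/E-RS are collected at Screening, Baseline and Month 7 and ask about the same day, so they are the most exposed. QOL-B and the respiratory PGI-S are collected at those visits and at Months 3, 5 and 6. Their one-week recall dilutes a same-day event.

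**Step 3: what one category is worth in one subject.**

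- QOL-B respiratory domain (SAP 9.3.2.1): score = (mean of 9 items − 1)/3 × 100. One category on one item = (1/9)/3 × 100 = 100/27 = 3.70 points. One category on both the cough and mucus items = 200/27 = 7.41 points.
- EXACT Cough & Sputum (SAP Table 5), raw 0 to 7: 0, 13, 25, 39, 56, 72, 86, 100. If items 2 and 3 each add one raw point (+2), the steps are 25, 26, 31, 33, 30, 28. Item 3 scores *A little* and *Some* the same (SAP Appendix C), so a move between those two adds nothing and only item 2 contributes (+1). Item 3 then scores 1, so the starting raw score is 1 to 4 and the steps are 12, 14, 17, 16. The full range is 12 to 33 points.

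**Step 4: from one subject to a group.** Let s be the average shift per induced subject. The effect on mean change is (share induced before PROs at Month 7 − share at Baseline) × s. The effect on the converter contrast is the difference in that quantity between converters and non-converters. The documents give neither the shares nor s. If the shares are equal at both visits, mean change does not move; if they change equally in both groups, the converter contrast does not move.

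**The case against.** The case against has several good points.

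- **The route to the clinic.** The sentence in 8.1 telling a subject to come in for induction follows advice on backing up non in-clinic visits, which are Months 2 and 4 and have no PROs. That stands, and the point does not rest on it. It rests on the general permission to induce, which covers every visit, and on the visit-day sample in footnote m.
- **Direction.** A reader might infer that the affected subjects are mostly those who have improved, so that change is biased toward zero. The documents do not support this. They give no induction rates by visit, arm or conversion status. Inclusion criterion 10 already allows induction at Screening. A non-productive visit before conversion counts as culture positive (8.1), so subjects with little sputum can be classed as non-converters.
- **Concurrent validity.** A reader might infer that improvement by Month 7 weakens the EXACT/E-RS correlations. It cannot, because concurrent validity is assessed at Baseline (10.5.2). Induction at Baseline could distort those correlations, but in either direction, since QOL-B and EXACT could shift together.
- **The anchor.** The respiratory PGI-S is exposed too. PRO and anchor could move together, so the net effect on the meaningful-change estimate is unclear.
- **Unseen material.** The site laboratory manual and the eCRF may already set an order or record sample type. This cannot be checked here.
- **Residual exposure.** Sputum coughed up spontaneously before the PROs would remain exempt, although EXACT item 3 asks about mucus that day. True, but that is the subject's own expectoration, which is closer to what the item is meant to capture.

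None of this closes the gap: the protocol sets no order between induction and the PROs.

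**Conclusion.** The point holds as an ordering gap. The exception is wider than its stated reason, and in-clinic induction immediately before cough and mucus items is allowed as written. The result is avoidable error in PRO change, chiefly in EXACT/E-RS. There could be bias if induction frequency differs between Baseline and Month 7 or by conversion status. Size and direction are unknown.

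The 3.7-point and 12-to-33-point figures show what one category is worth in a single affected subject. They assume that induction moves an answer by a full category, which the documents do not say. Two stronger quantitative readings should be resisted. Setting 7.4 points in one subject against the 7-point planning difference compares an individual shift with a difference in group means. Multiplying an assumed 10 to 40 percentage-point excess of induction in converters by 3.7 to 7.4 points gives 0.37 to 2.96 points of bias, but both factors are assumptions and the items have one-week recall. That product is not an estimate.

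This is a cheap improvement to measurement quality in a PRO validation study, not a flaw that invalidates an analysis.

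**What to change.** In Protocol 6.1, Table 4 footnote e and 7.1.1, limit the exception to sputum produced spontaneously. State that any in-clinic induction at a PRO visit follows the last PRO (PGI-S Fatigue) and precedes study drug. This fits the existing sequence, because Section 5.1.4 already makes ALIS/ELC the last procedure of the visit.

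Record sample type and collection time if they are not already captured. Flag PRO sets completed after induction. Repeat the Month 7 PRO change analysis without flagged sets, and do the same for the Baseline concurrent-validity analysis if any Baseline sets are flagged. If the protocol can no longer be changed, a flag built from source times, where these exist, and the sensitivity analysis are still worth having.

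Cost: induced subjects wait while the PROs are completed. On the Section 6.1 time estimates this is 10 + 8 + 3 + 3 + 10 + 8 + 1 + 1 = 44 minutes to 15 + 12 + 3 + 3 + 10 + 12 + 1 + 1 = 57 minutes, so up to about an hour. Add wording changes in three places, an eCRF entry for sample type and time if needed, and one sensitivity analysis. No extra procedure is required.
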